Impact of Behavioral Treatment of Insomnia on Nighttime Urine Production

University of Pittsburgh STUDY19110063

NCT03883724

INTRODUCTION

Nocturnal polyuria (NP) has long been known to be a major contributor to nocturia in the elderly. NP has a strong bidirectional relation with poor sleep especially in the elderly; however, to the best of our knowledge, an intervention directed solely at sleep has never been tried for NP. Our previous studies have shown that improving sleep with BBTI improves nocturia. However, we do not know the mechanisms by which behavioral sleep treatments improve nocturia. The proposed study will be the first to directly examine two plausible mediators: first uninterrupted sleep period (FUSP) and NP. The knowledge gained from this study can help identify 1) impact of sleep intervention on nighttime urine production, and 2) mechanisms by which sleep intervention improves nocturia

STUDY OVERVIEW

This pilot study will provide critical preliminary data regarding the relation between sleep and nighttime urine production in seniors by: 1) examining the impact of behavioral sleep treatment (BBTI- brief behavioral treatment of insomnia) on nighttime urine production- NP and 2) exploring the potential mechanisms by which BBTI impacts nocturia. To address the proposed aims we will perform a randomized controlled pilot trial of 60 healthy community-dwelling men and women aged 65 and over with nocturia and NP. The participants will be randomized to receive the 4-week behavioral sleep intervention BBTI by a trained therapist or an information control intervention. The participants will undergo detailed sleep and bladder assessments pre- and post-intervention to assess the effect of treatment. Data from this study will provide feasibility and pilot data for a subsequent, larger, and more definitive trial.

Outcome measures:

- 1) Change in NP- measured by NPi- nocturnal polyuria index=(nocturnal urine volume/24-hour volume)*100
- 2) Change in nocturia frequency
- 3) Change in FUSP or duration of uninterrupted sleep before the first awakening to void

STUDY FLOW /STUDY PROTOCOL

Study Flow Chart					Post-intervention assessment		
Screening		Baseline assessment		Intervention			
		Visit 1	In-home Assessments	BBTI			
				Session			
Telephone Screening		Apnea Link Plus®	Detailed history & physical	Wk 1	Wk 1 Sleep/ Bladder diary Z-machine ISI		
				Tele call	Tele call		
		IC	Sleep/ Bladder diary Z-machine ISI	Wk 2	Wk 2 Tele call		

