				Wk 3	Wk 3 Tele call		
				Wk 4	Wk 4 Tele call		

Screening

Screening procedures include: a) telephone interview and b) Visit 1 to study research suite - Continence Research Unit at UPMC Montefore Hospital. If the subject is interested and qualifies, then the other visits are scheduled.

Telephone Interview

Use IRB approved telephone script to determine eligibility (5-20mins; study nurse/coordinator) ApneaLink mailed to participants who screened eligible upon telephone interview

Visit 1

2 hour; study nurse; in-person

1. Obtain informed consent and sign document.
2. Questionnaires:
 - Medical and Surgical history
 - Current medication
 - Current incontinence
 - ISI
 - MoCA (paper)
3. Uroflow and dip (at appropriate bladder fullness)
4. Measure flow rate and volume of normal void
5. Post-void residual measurement by ultrasound
6. Physical examination: Short physical examination.
7. Sleep/ bladder diary: Explain 3 day sleep and voiding diary instructions.
8. Zmachine: watch instruction video. The device to be worn on the 3rd night of voiding diary
9. Schedule visit 2 with enough time to complete diary.

Visit 2

Randomization

1. Follow study procedure according to the group randomized to.

Telephone follow-up

Week 2 after the visit 2- both groups (BBTI and Control)

Week 4 after the visit 2- both groups

Visit 3

For participants randomized to BBTI group

Post intervention

4 weeks post visit 2

1. Sleep/ Bladder diary (send in mail)
2. Zmachine (send in mail)
3. ISI- completed telephonically.

Inclusion/exclusion criteria

For this study researchers shall enroll: ambulatory and functionally-independent community-dwelling men and women aged 65+ years, with nocturia ≥ 2 /night.

Exclusion criteria:

- Unstable or acute medical or central nervous system conditions
- Untreated, current, severe psychiatric condition
- Untreated, current, severe overactive bladder syndrome
- Post void residual $> 30\text{ml}$
- Sleep apnea with $\text{AHI} \geq 15$
- Currently diagnosed and/or treated Obstructive Sleep Apnea, Restless Legs Syndrome, parasomnia
- CHF, by exam or NT-proB natriuretic peptide (NT-proBNP) $> 30 \text{ pmol/L}$
- Chronic kidney disease, stage III-V (eGFR < 60)
- > 14 alcohol drinks per week
- > 3 caffeinated drinks ($\sim 300\text{mg}$) per day

Statistical Analysis Plan

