Randomization: After all baseline assessments are complete, researchers will randomize the participants in to the intervention groups in a 1:1 ratio, with random block sizes chosen from small even numbers, stratified by severity of baseline nocturia (≤ 3 or > 3 /night). To prevent educated guessing, the study statistician will reveal exact details of blocking strategy only at study completion.

Data Analysis: In addition to statistical significance, researchers will employ descriptive statistics and graphical techniques to draw conclusions. Specifically, as appropriate for a pilot study, researchers will focus interpretations on magnitudes of effects from standard statistical methods rather than their p-values, and apply graphical techniques such as needle plots to represent data at the individual level rather than based on averages. Researchers will use SAS® version 9.3 (SAS Institute, Inc., Cary, North Carolina) software, intention-to-treat philosophy, and multiple imputation for missing data in all inferential analyses.

First, researchers will compare baseline characteristics between the group using independent samples t-, Wilcoxon rank sum, chi-square and Fisher's exact tests, as appropriate. Any significant differences will be used as additional covariates in sensitivity analyses. Second, researchers will fit a series of analysis of covariance (ANCOVA) models with pre- to post-intervention change in each outcome as the dependent variable, intervention group as the independent factor of interest, and baseline value of outcome as a covariate. Magnitude and significance of intervention group term will serve as evidence for Aim 1 efficacy hypotheses. Third, for Aim 2, researchers will begin by exploring correlations of pre- to post-intervention changes in nocturia with those in FUSP and NPI. In keeping with Baron and Kenny's framework for mediation analysis, researchers will add FUSP change and NPI change (both individually and together) as additional independent variables to the Aim 1 ANOVA models. Any subsequent reduction in intervention effect will be interpreted as supporting the Aim 2 mediation hypotheses. Statistical significance of the extent of mediation will be obtained using %SOBEL, %INDIRECT and %MEDIATE SAS® macros, as appropriate.

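### In Aim 2, a longer FUSP can reflect lower night urine production rather than better sleep, so shrinkage after adding FUSP change does not by itself show a sleep mechanism

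*Combined protocol and SAP*

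**What the plan says.** The Introduction presents the study as the "first to directly examine two plausible mediators: first uninterrupted sleep period (FUSP) and NP". The Outcome measures list defines the three quantities that enter Aim 2:

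- urine production: "nocturnal polyuria index=(nocturnal urine volume/24-hour volume)*100";
- the mediation outcome: "Change in nocturia frequency";
- the sleep-side mediator: "Change in FUSP or duration of uninterrupted sleep before the first awakening to void".

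At Visit 1 the diary entry reads "Explain 3 day sleep and voiding diary instructions", and the Zmachine entry adds "The device to be worn on the 3rd night of voiding diary".

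In the SAP (Data Analysis), Aim 2 starts from correlations between the changes in nocturia, FUSP and NPi. Then "researchers will add FUSP change and NPI change (both individually and together) as additional independent variables" to the Aim 1 models. Any fall in the intervention effect after that step is to be taken as support for the mediation hypotheses, with significance from SAS mediation macros. The plan does not mention that FUSP and nocturia share a void, sets no order between the two mediators, and names no sleep measure for Aim 2 other than FUSP.

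**The concern.** The two mediators are meant to stand for two routes to less nocturia: better sleep (FUSP) and less urine at night (NP). By its definition, however, FUSP is closed by a void. If the bladder fills more slowly, the first void comes later and there are fewer voids. FUSP lengthens and nocturia falls together, with no change in sleep. When FUSP change is then added to the nocturia model, it takes over part of the group effect because it is partly another reading of the same events.

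Under the SAP's rule that shrinkage is support for mediation. A treatment acting only through urine production could therefore be reported as acting partly through sleep. The SAP directs interpretation to effect magnitudes, and this is a bias in the magnitude, so it would carry into the larger trial that the pilot is meant to inform.

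**Working it through.** The documents give no figure on this point and no physiological parameters, so there is nothing to reproduce. The check is a simulation of the SAP's own models.

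**Inputs from the documents.** 60 participants, 1:1 allocation, 3-day diary before and after, nocturia of at least 2 per night at entry, and the definitions of FUSP and NPi above. The counting rule for nocturia is not given; it is taken as the number of night-time voids.

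**Assumptions, not in the documents.** Night production about 110 ml/h, bladder capacity about 270 ml, sleep period about 7.5 h, spontaneous awakenings 0.15/h (with a void if the bladder is more than 40% full), day volume about 1000 ml, NPi of at least 33% at entry, and between-person and night-to-night variation. A void-free night is given FUSP equal to the sleep period. Simulated baseline: about 3.4 voids, FUSP about 2.0 h, NPi about 48%. There were 400 trials per scenario.

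**Models.**
- Total effect c: group term in nocturia change ~ group + baseline nocturia.
- Remaining effect c′: the same model plus FUSP change (coefficient b), NPi change, or both.
- Path a: group term in FUSP change ~ group + baseline FUSP.
- Cut = 1 − c′/c. FUSP share in the joint model = a × b(joint) / c.
- Sobel z = ab / √(a²·SE_b² + b²·SE_a²), significant if |z| > 1.96.

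**Results** (effects in voids per night; percentages come from unrounded values, so hand arithmetic can differ by a point).

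| Scenario | c | c′ with FUSP | Cut | Sobel, FUSP alone | Cut, NPi alone | FUSP share, joint | Sobel, joint |
|---|---|---|---|---|---|---|---|
| Urine −10%, sleep unchanged | −0.36 | −0.18 | 49% | 26% | 53% | 35% | 20% |
| Urine −20%, sleep unchanged | −0.70 | −0.36 | 49% | 76% | 57% | 34% | 64% |
| Urine −30%, sleep unchanged | −1.07 | −0.57 | 47% | 99% | 55% | 32% | 85% |
| Urine −20%, no spontaneous awakenings | −0.73 | −0.27 | 63% | 91% | 57% | 43% | 83% |
| Sleep only (awakenings × 0.3, from 0.3/h) | −0.35 | −0.16 | 54% | 25% | 1% | 39% | 18% |
| No treatment effect | 0.00 | 0.00 | – | 4% | – | – | 3% |

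Worked row, urine −20%: FUSP lengthens by a = 0.45 h although sleep is unchanged. The cut is 1 − 0.36/0.70 = 49%. In the joint model b = −0.53, so the FUSP share is 0.45 × 0.53 / 0.70 = 34%. The cut from NPi alone is 1 − 0.30/0.70 = 57%.

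The group effect shrank on adding FUSP in 90% of trials at a 10% fall and in about 100% at 20% and 30%. With no treatment effect, the changes in nocturia and FUSP were still correlated at about −0.61. The SAP's first step would therefore show a strong association whatever the mechanism.

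**Sensitivity to the assumed physiology.** Other bladder-filling simulations with different settings, again at a 20% fall with sleep unchanged, gave FUSP alone 33%, 34%, 40% and 44% of the effect. Three of these (33%, 40% and 44%) also gave a joint-model share: 29%, 37% and 36%. NPi alone explained 39–44% under urine-only and 0–1% under sleep-only. With voids placed at random and their rate cut by 20–40%, adding FUSP still shrank the effect by 25–28%.

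**The case against.** A reader might infer that the trial cannot tell its two mechanisms apart. The documents do not support that. The SAP fits a model for change in each outcome, NPi included, and enters NPi individually as well as jointly with FUSP. The NPi-alone model does discriminate (1% against 53–57% in the table). What is missing is a rule for reading FUSP beside NPi.

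A reader might also infer that any fall in urine production produces false mediation, or that shrinkage is bound to occur. Neither holds. The fall must be larger in the BBTI arm: with no between-arm difference, Sobel was significant in only 4% of trials. At a 10% fall the effect shrank in 90% of trials, but Sobel was significant in only 26%. Where the true route is sleep, shrinkage is the right answer.

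Nor is Aim 2 the sole reason for the study. The title and the first stated purpose concern night-time urine production; mechanisms are a second, exploratory purpose of a pilot. That lowers the stakes but does not remove the point, because the SAP asks for interpretation by magnitude and the magnitude is what is biased.

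It can fairly be said that a later first void is, literally, longer uninterrupted sleep. The error lies in reading it as a mechanism separate from urine production. Timing sleep with the Zmachine would not break the link while FUSP still ends at a void.

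A substitute sleep measure has its own weakness. Wake time not linked to a void, for example, needs void times to classify each awakening. In sleep-only simulations with 60 participants it reached Sobel significance in 3–21% of trials, against 18–48% for FUSP, and carried only 19–27% of an effect that was entirely due to sleep. This stands, and it shapes the fix.

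**Conclusion.** The concern holds for the interpretation rule, which is wrong as written. A fall in night urine production that is larger in the BBTI arm lengthens FUSP and usually shrinks the group term, even with sleep unchanged, and the SAP would count that as mediation through FUSP. At a 20% fall with 60 participants, FUSP alone takes about 33–49% of the effect (63% if there are no spontaneous awakenings). Beside NPi it takes about 29–37% (43% in that same case), so the joint model reduces the artefact without removing it.

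The direction was the same in every urine-only scenario run. The percentages depend on assumed physiology and should not be quoted as estimates for this trial. The result also assumes that nocturia frequency is the count of night-time voids, including the one that ends FUSP. The change should be made, but the point does not undermine Aim 1 or make Aim 2 uninterpretable.

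**What to change.** In the SAP, Data Analysis, Aim 2:

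1. State that attenuation of the group effect after adding FUSP change, or a significant indirect effect through it, is not by itself evidence of a sleep mechanism separate from urine production.
2. Report the FUSP model as descriptive and read it only beside the NPi-alone and joint models. Allow for the order urine production → FUSP → nocturia, and say in advance what pattern would favour each route (for example, FUSP attenuates but NPi alone does not).
3. Add, as exploratory, a sleep mediator not defined by voiding: change in ISI or in a Zmachine sleep measure. The flow chart lists both before and after treatment. Use diary sleep-onset latency only if the diary records it, since no diary items are listed.

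Before relying on item 3, confirm that both arms are measured after treatment: the flow chart and overview indicate this, but the Visit 3 text places the diary, Zmachine and ISI under a line naming the BBTI group.

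Cost: SAP wording and one added exploratory model, with no new visits if both arms are measured as the overview describes. The FUSP mediation claim becomes weaker. The added measure may have low power with 60 participants (the Zmachine is worn on one night, and ISI is self-report), so a null result on it would not rule out a sleep route. A positive result would be only suggestive, because fewer voids may themselves improve sleep and both are assessed after treatment.

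### Aim 2 counts any fall in the group effect as support for mediation, a rule that cannot tell FUSP from NPi when the two changes are correlated

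*Combined protocol and SAP*

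**What the plan says.** The Introduction presents the study as the "first to directly examine two plausible mediators: first uninterrupted sleep period (FUSP) and NP". It also states that "NP has a strong bidirectional relation with poor sleep especially in the elderly".

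The Data Analysis paragraph of the Statistical Analysis Plan sets the base model for each outcome: change as the dependent variable, with "intervention group as the independent factor of interest, and baseline value of outcome as a covariate". For Aim 2, "researchers will add FUSP change and NPI change (both individually and together) as additional independent variables to the Aim 1 ANOVA models". One sentence then fixes the reading: "Any subsequent reduction in intervention effect will be interpreted as supporting the Aim 2 mediation hypotheses". The next sentence adds: "Statistical significance of the extent of mediation will be obtained using %SOBEL, %INDIRECT and %MEDIATE SAS® macros, as appropriate".

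The SAP does not say which of the three models governs attribution to FUSP or to NPi. It does not define a mediator-specific effect, or say what is concluded if the single and joint models disagree. It does not say to which model the macros will be applied.

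**The concern.** Aim 2 asks which of two candidate routes carries the effect of the sleep intervention on nocturia. The rule rests on the fall in the group coefficient, and that quantity does not answer the question in either kind of model.

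- In a single-mediator model, the omitted mediator confounds the slope of the one entered. If the two are correlated within arm, the entered variable borrows the other's effect.
- In the joint model, the fall is the sum of both routes and does not say which one contributed.

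The rule also has no threshold and needs no interval, so a chance fall counts as support. The trial could therefore report that both FUSP and NPi mediate the effect when only one does, and carry that conclusion into the larger trial that this pilot is meant to inform. The SAP puts magnitudes ahead of p-values, so the reduction rule is likely to drive the interpretation.

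**Working it through.** The plan gives no mediation figure to reproduce. The check is algebra, followed by a simulation of the stated design.

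**Inputs from the documents.** 60 participants (Study Overview), allocated 1:1 (Randomization), so 30 per arm; two mediators; three models; support means any reduction.

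**Assumed inputs.** The documents give no values for these. Effects are scaled so that benefit is positive. Group effect on each mediator a1 = a2 = 0.8 SD; active slope b1 = 0.5; inactive slope b2 = 0; direct effect c' = 0.2; mediator residual SD 1; error SD 1; within-arm correlation r = 0, 0.3, 0.5, 0.7; all 60 analysed. The baseline covariate is left out. If it is independent of the mediators, it does not change the expected reductions.

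**Formulas.**

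- Total group effect: c = c' + a1·b1 + a2·b2 = 0.2 + 0.8×0.5 + 0 = 0.60.
- Slope of the inactive mediator entered alone: b2 + r·b1 = 0.5r.
- Fall when it is entered alone: a2×(b2 + r·b1) = 0.8×0.5r = 0.4r. The true indirect effect is 0.
- Fall in the joint model: a1·b1 + a2·b2 = 0.40, whichever mediator carries it.

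**Results for the inactive mediator** (trial percentages from simulation; repeat runs agree to within about two points):

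| r | Expected fall, entered alone | Share of 0.60 | Trials with some reduction | Both paths significant, alone | Both paths significant, joint |
|---|---|---|---|---|---|
| 0 | 0.00 | 0% | about 50% | 5% | 5% |
| 0.3 | 0.12 | 20% | 84% | 15% | 4% |
| 0.5 | 0.20 | 33% | 96% | 35% | 5% |
| 0.7 | 0.28 | 47% | 99% | 58% | 5% |

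At r = 0 there is no systematic error, yet the rule as written is still met in about half of trials by chance.

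**Sobel test.** In a separate run with b1 = 0.6 and the baseline covariate included, the Sobel test for the inactive mediator entered alone was significant in 1.4%, 8.4%, 24% and 51% of trials at r = 0, 0.3, 0.5 and 0.7. From the joint model it was significant in about 1.5%. The joint model's specific effects were about 0.48 for the active mediator (0.8×0.6) and about 0.00 for the inactive one. The sign of the inactive one was still favourable in about half of trials.

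**Treatment does not move the inactive variable.** With a2 = 0 the expected fall is 0×r·b1 = 0 at any r.

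**Both variables active.** With b1 = b2 = 0.4, each single-mediator fall is 0.8×0.4×(1 + r). At r = 0.5 that is 0.48, against a joint fall of 0.64. The single-mediator falls overlap.

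**A sequential structure.** Suppose NPi acts through FUSP: NPi shifted 0.8, NPi→FUSP slope 0.5, FUSP slope on nocturia 0.5, and FUSP also shifted directly by 0.8 − 0.5×0.8 = 0.4. The total is again 0.2 + 0.5×0.8 = 0.60. The fall when NPi is entered alone is again 0.8×0.5×0.5 = 0.20, or 33%, but here it is a true indirect effect. The simulated pattern matches the r = 0.5 row: both paths significant in 35% of trials alone and 5% jointly. The data cannot separate the two structures.

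**The case against.** **The joint model is already planned.** It gives a FUSP coefficient adjusted for NPi and the reverse, and formal mediation macros are named. This stands. A reader might infer that the plan can yield only one combined reduction, and the documents do not support that. What is missing is any statement that the separate coefficients govern the conclusion. The macros are left to be used as appropriate, with no model specified, and do not displace the stated rule. Applied to single-mediator models, the Sobel test carries the same confounding.

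**Double-counting.** A reader might also infer that the two single-mediator reductions will be added, giving shares that exceed the whole. The SAP nowhere adds them or reports shares, and its rule speaks of the mediation hypotheses collectively. The overlap is real, but the summation is not planned.

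**The bias is conditional.** It needs within-arm correlation and a treatment effect on both variables. The Introduction's remark on sleep and NP, and the definition of FUSP by the first awakening to void, make correlation plausible. No figure is given, and the documents do not say which instrument yields FUSP. It cannot be asserted that a non-mediator will be credited, only that the rule does not guard against it.

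**The joint model as sole arbiter.** It is tempting to ask that support be judged from the joint model alone. The sequential case shows the cost: a genuine upstream mediator would fail to show a significant joint effect in about 95% of trials. Given the bidirectional relation that the Introduction describes, that structure cannot be excluded. This objection stands in full and shapes the fix.

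**Exploratory pilot.** Aim 2 is exploratory and Aim 1 is untouched. This lowers the stakes but does not make the rule informative.

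**Conclusion.** The concern holds as a fault in the decision rule. The models to be fitted are adequate; counting any reduction from any of them as support is not. If the two changes are correlated within arm and treatment moves both, a variable with no effect of its own on nocturia is expected to remove about 20%, 33% or 47% of the group effect at correlation 0.3, 0.5 or 0.7, and to satisfy the rule in 84%, 96% or 99% of trials of 60. At zero correlation the expected reduction is nil, though chance alone meets the rule in about half of trials. The joint reduction cannot be attributed to either variable.

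These sizes rest on the assumed path values, unit error SD and parallel mediators. The direction follows from algebra; the magnitude in this trial is unknown. The consequence is a misleading statement about mechanism. It is worth correcting before analysis.

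**What to change.** Replace the any-reduction sentence in the Data Analysis paragraph with an estimate-and-interval rule, for example:

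> From the model containing both FUSP change and NPi change, the specific indirect effect of each (group effect on the mediator times its slope on nocturia change) and their difference will be reported with bootstrap intervals, next to the single-mediator estimates. A reduction in a single-mediator model will not by itself be taken as evidence of a separate mechanism. Where a variable shows an effect alone but not jointly, the report will state that the data cannot distinguish a correlated non-mediator from a mediator acting through the other (for example NPi to FUSP to nocturia), and mediation will be neither claimed nor rejected for it.

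The SAP should also state to which model each macro is applied.

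Cost: wording only, with no new data and no new model. The bootstrap has to be combined with the multiple imputation already planned. Specific effects are less precise than single-mediator ones: in the simulation, the proportion of trials with both paths significant for the true mediator falls from about 82% to about 76% at correlation 0.5, and to about 64% at 0.7 (repeat runs differ by about one point). Some results will have to be declared indeterminate.

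### Aim 2 reads any fall in the group effect as support for mediation and plans no sensitivity analysis for confounding of the mediator-to-nocturia slope

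*Combined protocol and SAP*

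**What the plan says.** All the relevant text is under Statistical Analysis Plan, Data Analysis.

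- The Aim 1 models regress the pre-to-post change in each outcome on group and baseline: "intervention group as the independent factor of interest, and baseline value of outcome as a covariate".
- Aim 2 follows Baron and Kenny: "researchers will add FUSP change and NPI change (both individually and together) as additional independent variables to the Aim 1 ANOVA models".
- The decision rule sets no threshold: "Any subsequent reduction in intervention effect will be interpreted as supporting the Aim 2 mediation hypotheses".
- Formal tests are also planned: "Statistical significance of the extent of mediation will be obtained using %SOBEL, %INDIRECT and %MEDIATE SAS® macros, as appropriate".
- Weight is placed elsewhere, however: "researchers will focus interpretations on magnitudes of effects from standard statistical methods rather than their p-values".
- The only provision for further covariates concerns baseline variables that differ between arms: "Any significant differences will be used as additional covariates in sensitivity analyses".

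The plan names no common cause of mediator and nocturia. It does not state a no-unmeasured-confounding assumption, and it plans no sensitivity analysis for one.

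**The concern.** Participants are randomised to BBTI or control. They are not randomised to a change in FUSP or in the nocturnal polyuria index (NPI). The mediator-to-nocturia slope is therefore an observational association inside a randomised trial, and the fall in the group term when the mediator is added depends directly on it.

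The covariate provision does not cover this. It screens for imbalance between arms, whereas a common cause of mediator and nocturia can be perfectly balanced and still bias the slope.

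The documents give some reason to expect association without mediation. The Introduction describes a strong two-way relation between NP and poor sleep, so in each single-mediator model the omitted mediator is a plausible common cause. The Study Overview defines FUSP as ending at the first awakening to void, which ties it to a nocturia event. Visit 1 issues one combined 3-day sleep and voiding diary. The documents do not say that all three outcomes come from it, but if they do, one unusual or misrecorded night affects mediator and outcome together.

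At stake is the mechanism carried forward to the larger trial that this pilot is meant to inform. More participants would not remove the bias.

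**Working it through.** The plan states no alpha, effect size, SD or expected mediated share, so there is no figure to reproduce.

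**Inputs from the documents.** The study is a "randomized controlled pilot trial of 60 healthy community-dwelling men and women aged 65 and over with nocturia and NP", and researchers will "randomize the participants in to the intervention groups in a 1:1 ratio". That gives 60 / 2 = 30 per arm. The model holds group, baseline nocturia and the mediator change.

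**Assumed inputs.** Both changes are coded so that positive means improvement, with within-arm SD 1. BBTI shifts the mediator by a = 0.6 and nocturia by c = 0.6. The mediator has no effect on nocturia. The within-arm residual correlation rho comes only from shared causes or shared error, and is varied over both signs.

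**Step 1: size of the false effect.** In linear models with the same other covariates, total group effect minus direct group effect = a × b, where b is the fitted mediator slope. With unit SDs and an inert mediator, b is about rho. The false mediated share is therefore a × rho / c:
- rho = 0.2: 0.6 × 0.2 / 0.6 = 20%
- rho = 0.3: 0.6 × 0.3 / 0.6 = 30%

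**Step 2: how often the group term falls, by hand.** It falls when the estimates of a and b have the same sign.
- SE(a) = √(2/30) = 0.258, so P(estimated a > 0) = Φ(0.6/0.258) = 0.990.
- At rho = 0.2, SE(b) ≈ √(0.96/56) = 0.131, so P(estimated b > 0) = Φ(0.2/0.131) = 0.937. The group term falls with probability 0.990 × 0.937 + 0.010 × 0.063 = 0.93.
- At rho = 0.3, SE(b) ≈ √(0.91/56) = 0.127 and P(estimated b > 0) = 0.991. The group term falls with probability 0.98.
- At rho = 0, the estimate of b is symmetric about zero, so the answer is one half.

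**Step 3: simulation of the same set-up.** Counting a fall in the absolute group effect gives slightly lower figures, because the adjusted term sometimes overshoots zero.

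| rho | Share apparently mediated | Trials in which the group term falls |
|---|---|---|
| -0.3 | -30% | 2% |
| -0.2 | -20% | 8% |
| 0 | 0% | 49% |
| 0.2 | 20% | 91% |
| 0.3 | 30% | 96% |

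**Step 4: other effect sizes (c = 0.5).** At rho = 0.3 the group term falls in 84%, 93% and 93% of trials for a = 0.3, 0.5 and 0.8. If BBTI does not move the mediator (a = 0), it falls in about 50% whatever rho is.

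**Step 5: which causes matter.** With separate pre and post waves, a stable trait shared by mediator and nocturia leaves the rate at 49–50%, because it cancels in the change scores. Wave-specific shared state or diary error with correlation 0.3–0.5 raises it to 84–93%.

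**Step 6: which part of the plan causes what.** With c = 0.5, a = 0.5 or 0.8 and rho = 0.3 or 0.5, adjusting for the simulated common cause itself brings the median false share from 27–76% to about 0%. Sobel false positives drop from 13–76% to 1–3%, and bootstrap ones from 32–86% to 4–6%. The any-reduction rule still flags the inert mediator in about 50% of trials. With two inert mediators and no confounding, at least one of the three planned models shows a reduction in 74%. The bias and the rule are separate faults.

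**The case against.** A reader might infer that an inert mediator will usually look like a mediator in this trial. The documents do not support that. It needs BBTI to move the mediator, a common cause acting in the same direction as treatment, and reliance on the any-reduction rule. The documents supply only the last. If the common cause acts against treatment, the group term rarely falls.

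A reader might also infer that any shared cause is enough. It is not: stable additive causes cancel in change scores. What remains is time-varying states, shared recording error, and traits that alter the change itself.

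Nor is the plan without adjustment. Baseline nocturia is a covariate, the joint model adjusts each mediator for the other, and a limited covariate sensitivity analysis exists.

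The formal tests offer some protection. In the 0.6 SD setting both paths reach significance in about 20% and 40% of trials at rho = 0.2 and 0.3, a minority. Sobel p < 0.05 occurs in 4%, 13% and 35% at rho = 0.3 for a = 0.3, 0.5 and 0.8 (c = 0.5).

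Finally, the Study Overview presents Aim 2 as exploring possible mechanisms in a pilot.

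These points narrow the concern but do not dispose of it. The plan puts magnitudes ahead of p-values, and the magnitude is what confounding biases. The stated rule works without any test.

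**Conclusion.** The concern holds in a conditional form. As written, Aim 2 can report support for a mediator that does nothing. It probably will if BBTI moves that mediator and a time-varying common cause, shared diary error or change-altering trait acts in the treatment direction.

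With 30 per arm, 0.6 SD effects on both and residual correlations of 0.2 to 0.3, the false mediated share is 20% to 30% and the group term falls in 91% to 96% of trials. At zero correlation the rule is a coin toss, and at negative correlations it errs the other way, hiding mediation instead of inventing it. The effect sizes and correlations are assumptions, so the direction and size in this trial are unknown.

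The exploratory, pilot status of Aim 2 lowers the severity. The change is still worth making before analysis.

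**What to change.** 1. **Replace the decision rule.** Report the indirect effect with a confidence interval for each mediator, and drop the statement that any reduction supports mediation.

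2. **Add a sensitivity analysis.** For each single-mediator model, report the indirect effect over a range of residual correlations of both signs. Let r be the observed correlation between the residuals of the arm-adjusted mediator and nocturia models (with baseline nocturia in both), and s_M and s_Y their residual SDs. At an assumed rho the indirect effect is a × (s_Y/s_M) × {r − rho × √[(1 − r²)/(1 − rho²)]}, which is zero at rho = r. Report r with its confidence interval. At n = 60 this is wide: 1.96/√(60 − 3 − 2) = 0.264, or about ±0.26 near zero. For the joint model, state that each mediator is adjusted for the other and give the corresponding partial correlation.

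3. **State the assumption.** Say that Aim 2 assumes no unmeasured mediator-outcome confounding, and word any mechanism conclusion as conditional on it.

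Items 1 and 2 are both needed. An interval alone still has a biased centre, and a sensitivity curve alone leaves the coin-toss rule in place.

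Optionally, add age, sex, AHI and post-void residual as a further sensitivity analysis. They help only if they predict change. The exclusion criteria restrict the range of AHI and post-void residual, and nothing here shows that this set would remove the bias.

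The cost is SAP wording, a little more analysis and a more cautious Aim 2 conclusion. Residual confounding is made visible, not removed.
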